## 2.1. Risk Benefit Assessment

5HT3-RAs and NK1-RAs are among the drugs of first choice for an optimal antiemetic prophylaxis in cancer patients receiving chemotherapy.

Akynzeo® contains two active substances: Netupitant, a NK1-RA, and Palonosetron, a 5HT3-RA, thus representing a valid and convenient therapeutic option associated with improvement of patient's compliance.

The clinical development program consistently demonstrates that Akynzeo® with dexamethasone provides additional benefit in terms of complete response, both in the delayed, the acute, and the overall phases of CINV in both cisplatin-based chemotherapy (HEC) and AC based chemotherapy (formerly defined as MEC and more recently re-classified as AC HEC).

A single oral dose administered on Day 1 of HEC and MEC regimens is adequate to protect patients from both acute and delayed CINV, as pharmacologically predicted.

The fixed dose combination was shown to be safe and well tolerated in single and multiple cycle studies and there was no increase in AEs observed after repeated cycles. Adverse events most commonly reported were those associated with cytotoxic effects of chemotherapy, or the underlying malignancy. Only headache and constipation, known class effects of the 5-HT3 RAs and NK1 RA, were considered drug-related.

Post-marketing data also provide safe foundation for confident administration of this medicine.

CONFIDENTIAL

Confidential	MyRisk	Date: 05 February 2024
	Protocol	
	PROTOCOL NUMBER: IBA1160	Version: 5.1

Potential safety concerns include teratogenic effects, serotonin syndrome and Torsade de pointes due to QT/QTc prolongation.

The potential of a teratogenic effect of netupitant in humans is limited and based solely on the preclinical findings observed in rabbits and rats. The incidence of cleft palate in rats occurred at exposures approximately 7-fold greater than exposures seen in humans. Preclinical data showed that palonosetron did not affect pre- or postnatal development, except at high oral doses, unrepresentative of the clinical situation. No substantial evidences are available in clinical studies; therefore, the likelihood of teratogenic effects may represent a safety concern. To mitigate this potential risk advice is given to female patients concerning fertility and pregnancy in the SPC.

The occurrence of Serotonin Syndrome, a potentially life-threatening drug reaction, has been considered a potential class effect of the anti-emetics belonging to the class of the 5HT3 RAs, which includes palonosetron. An increased risk might be evident if antiemetics are administered in combination with other serotonergic agents. The prospective of an increase in use of Akynzeo® in different cancer settings, also in combination with other serotonergic drugs, makes the issue of the risk profile important for these drugs. Patient safety would be served if serotonin syndrome is mentioned in the product labelling; therefore, the authorities recommended update of the labelling to inform about this risk.

Torsade de pointes is the most important clinical outcome of QT/QTc prolongation. Integrated review of all available nonclinical and clinical data suggests that Akynzeo® is devoid of any effect on QTc interval or of a proarrhythmic potential. No events of QT prolongation attributable to Akynzeo® have been reported during the post-approval phase. Nevertheless, since cancer patients are a vulnerable population receiving potentially cardiotoxic antineoplastic agents, or with medical history remarkable for hypothyroidism or cardiac diseases on treatment with antiarrhythmics, or may carry electrolytes imbalance, it is reasonable to consider Torsade de pointes due to QT/QTc prolongation an important potential risk. To mitigate this risk, in the SPC an advice is given for monitoring of patients with conditions leading to QT prolongation.

In conclusion, the available efficacy and safety data originated from the clinical development program and the post-marketing experience are suggestive of a favourable benefit-risk profile of Akynzeo®.

CONFIDENTIAL

Confidential	MyRisk	Date: 05 February 2024
	Protocol	
	PROTOCOL NUMBER: IBA1160	Version: 5.1

## 2.2. Study Objectives

### Primary objective:

1. To evaluate if the use of NEPA (netupitant and palonosetron) in patients treated with IV moderately emetogenic chemotherapy and at high risk of CINV is more effective in preventing CINV than standard of care antiemetics, during the overall phase (0-120 hours) post-chemotherapy, over three cycles of chemotherapy

### Secondary objectives:

2. Evaluate acute (0 to 24 hours), delayed (>24 to 120 hours), and overall (0-120 hours) CINV indicators in each cycle of chemotherapy

Time 0 is defined as the start time of the chemotherapy administration on Day 1 of each of the three cycles. CINV indicators are nausea and vomiting, their intensity and frequency and Quality of Life in the acute, delayed and overall period.

3. Evaluate the predictive role of potential risk factors in the development of CINV over three cycles of chemotherapy

Potential risk factors for CINV are those thought to be increasing the risk of CINV in patients receiving MEC reported in section 3.3.3. Risk factors for CINV and in section 3.6.3.1 where the risk score algorithm calculation by using predictive factors for CINV is explained.

4. Evaluate the safety profile of the antiemetic drug over three cycles of chemotherapy

5. Explore the effect of CINV on daily activities and quality of life in patients receiving moderately-emetogenic chemotherapy over three cycles of chemotherapy

6. Evaluate resource utilization and health economic outcome

## 3. Methodology

### 3.1. Design

This is a phase IV interventional, open label, randomized, active controlled, parallel arms, multicenter and multinational study.

Akynzeo® will be used in compliance with its Summary of Product Characteristics (SPC).

Standard of care will be used according to SPC and will reflect the consensus of experts in the evidence-based guidelines of MASCC/ESMO resulting from systematic reviews of the published trials of the last two decades.

### 3.2. Sample and settings

Adult patients, aged  $\geq 18$  years, naïve and non-naïve to chemotherapy, with diagnosis of any cancer scheduled and intended to be treated for at least three consecutive cycles with single doses of any IV MEC regimen per cycle who are able to comply with study requirements and giving signed Informed consent.

CONFIDENTIAL

Confidential	MyRisk	Date: 05 February 2024
	Protocol	
	PROTOCOL NUMBER: IBA1160	Version: 5.1

### 3.3. Patients' Selection Criteria

#### 3.3.1. Inclusion Criteria

- Adult patients aged  $\geq 18$  years
- Patients with a risk score of  $\geq 13$  as calculated by the algorithm – see 3.6.3.1. Baseline/screening: VISIT 0
- Signed Informed consent
- Patients with diagnosis of any cancer scheduled and intended to be treated for three consecutive cycles with a single dose of any IV MEC regimen, per cycle, including adjuvant or neo-adjuvant chemotherapy
- Patients with ECOG performance status 0, 1 or 2
- Use of Standard of Care defined as a 5-HT3 RA + Dexamethasone (or equivalent corticosteroid) based-regimen on day 1 of chemotherapy for CINV prevention
- Naïve and non-naïve to chemotherapy
- The enrolled women should be a) of non-childbearing potential or b) of childbearing potential using reliable contraceptive measures and having a negative urine pregnancy test done by health care team within 1-24 hours before dosing the antiemetic treatment in both arms and outcome recorded in the medical records
- Able to comply with study requirements

IV Moderately Emetogenic Chemotherapy (MEC) includes any of the following chemotherapy drugs:

-

Alemtuzumab Azacitidine Bendamustine Carboplatin Clofarabine Cyclophosphamide $< 1500$ mg/m $^2$ Cytarabine $> 1000$ mg/m $^2$	Daunorubicin Doxorubicin Epirubicin Idarubicin Ifosfamide Irinotecan	Oxaliplatin Romidepsin Temozolomide Thiotepa Trabectedin
--	---	--

**Birth control methods which may be considered as highly effective:**

Methods that can achieve a failure rate of less than 1% per year when used consistently and correctly are considered as highly effective birth control methods. Such methods include:

- combined (estrogen and progestogen containing) hormonal contraception associated with inhibition of ovulation:
  - oral
  - intravaginal
  - transdermal
- progestogen-only hormonal contraception associated with inhibition of ovulation 1:
  - oral
  - injectable
  - implantable
- intrauterine device (IUD)
- intrauterine hormone-releasing system (IUS)
- bilateral tubal occlusion
- vasectomised partner
- sexual abstinence

**Acceptable birth control methods which may not be considered as highly effective:**

Acceptable birth control methods that result in a failure rate of more than 1% per year include:

- progestogen-only oral hormonal contraception, where inhibition of ovulation is not the primary mode of action
- male or female condom with or without spermicide
- cap, diaphragm, or sponge with spermicide

Considering Akyenzeo® during the non-clinical study does not indicate teratogenicity/fetotoxicity in early pregnancy and human data are not available or do not contradict these findings, the inclusion of WOCBP is possible using at least acceptable effective contraceptive measures.

**Recommendations for male subjects with pregnant or non-pregnant WOCBP partner:**

Considering the Study genotoxicity of IMP the male contraception (condom) is recommended to avoid exposure of an existing embryo/fetus. Contraception should be continued until the end of relevant systemic exposure in WOCBP.

**Contraception after the end of treatment:**

Contraception should be continued until the end of relevant systemic exposure in WOCBP. The end of relevant systemic exposure is defined as the time point where the IMP, including any active or major metabolites, has decreased to a concentration that is no longer considered relevant for human teratogenicity/fetotoxicity.

### 3.3.2. Exclusion Criteria

- Patients receiving highly emetogenic chemotherapy (including anthracycline+cyclophosphamide-based chemotherapy)
- Patients receiving oral moderately emetogenic chemotherapy drugs
- Patients receiving opioids within 2 weeks prior to trial enrollment (longer use allowed)
- Use of olanzapine as prophylaxis of CINV

CONFIDENTIAL

Confidential	MyRisk	Date: 05 February 2024
	Protocol	
	PROTOCOL NUMBER: IBA1160	Version: 5.1

- Patients scheduled to receive radiotherapy concurrently with chemotherapy
- Any illness or condition that, in the opinion of the physician, may confound the results of the study or pose unwarranted risks in administering the investigational product to the patient.
- Patients with mechanical risk factors for nausea (i.e. intestinal obstruction)
- Patients with liver disease (as nausea is a common presenting symptom)
- Patients with metabolic risk factors for nausea (i.e. electrolyte imbalances causing nausea/vomiting)
- Chronic treatment with steroids (with the exception of inhaled or topical steroids)
- Pregnancy and/or breast-feeding women
- Women of childbearing potential refusing to use effective contraception during the whole study treatment and up to one month after study treatment with Akyenzeo®
- Use of Standard of Care including an NK-1 RA-based regimen to prevent CINV

### 3.3.3. Risk Factors for CINV

At the time of the collection of demographic and medical history data at the screening visit (Visit 0, see details below), all the predictive individual factors will be collected and the patients' risk score automatically calculated. These parameters will be used to identify the patients with a CINV risk score  $\geq 13$  (see 3.3.1., Inclusion Criteria). If the patients comply with all the inclusion and exclusion criteria, they are enrolled into the study. The parameters from 1 to 7 will be used to identify the patients at high risk of CINV:

1. Nausea and/or vomiting in the prior cycle of chemotherapy
2. Use of non-prescribed antiemetics at home in the prior cycle of chemotherapy
3. Platinum or anthracycline-based chemotherapy
4. Age  $< 60$  years
5. Expectation for (anticipating) nausea and/or vomiting
6. History of morning sickness during previous pregnancy
7. Cycle of chemotherapy
8.  $< 7$  h of sleep the night before chemotherapy (to be obtained at day of chemotherapy)
9. History of any nausea and vomiting such as motion sickness, vestibular dysfunction...
10. Anticipatory nausea and/or vomiting
11. Anxiety over the past 24hrs (to be obtained at day of chemotherapy)
12. Alcohol intake (number of units per week)
13. Gender
14. Fatigue experience (symptom)
15. Smoking status
16. Weight

Parameters from 8 to 16 are defined as additional risk factors and will not influence the risk score.

The risk factors for CINV are checked at each cycle before chemotherapy and are used for patient's risk score re-calculation. This result of the re-calculation has no impact on patient's participation in the study and the randomized group.

The percent of patients using carboplatin will be limited to 20% of the planned number of patients in the study: the maximum number of patients using carboplatin in this study will be 106.

CONFIDENTIAL

Confidential	MyRisk	Date: 05 February 2024
	Protocol	
	PROTOCOL NUMBER: IBA1160	Version: 5.1

### 3.4. Intervention and Antiemetic Treatment

Eligible patients will receive before the start of cycle 1 in ratio 1:1 and be assigned either to ARM A (test arm) or ARM B (control arm):

#### ARM A: NEPA

- One capsule of Akynzeo®, a fixed-dose oral combination (NEPA) of the NK1 Receptor Antagonist (RA) netupitant (300 mg) and of the 5-HT3 RA palonosetron (0.5 mg) + Dexamethasone 8 mg (or equivalent corticosteroids) by the oral route on Day 1, approximately 1 hour before chemotherapy

#### ARM B: Standard of care

- Dexamethasone (or equivalent corticosteroids) 8 mg administered by the oral route (or equivalent IV dose) on Day 1, approximately 1 hour before chemotherapy and one of the 5-HT3-RAs recommended by ESMO and MASCC guidelines (standard of care), i.e. either:

Granisetron, 2 mg (oral) or 1 mg (IV)

OR

Palonosetron, 0.5 mg (oral), 0.25mg (IV)

OR

Ondansetron, 16 mg (oral) or 8 mg (IV)

Akynzeo® will be provided at national level to each center in a sufficient number of units to cover the need of the enrolled patients' treatment. IMPs will be sourced locally by site pharmacy.

The drugs that may be used as standard of care in Arm B, including dexamethasone that is also used in Arm A, are investigational medicinal products (IMPs) for this study.

The 5-HT3-RAs and dexamethasone (or equivalent corticosteroid) will be provided by the centers as per usual routine practice.

In patients receiving moderately emetogenic chemotherapy (i.e.: oxaliplatin, anthracycline and cyclophosphamide) with known potential for delayed nausea and vomiting, the use of dexamethasone (or equivalent corticosteroid) for days 2 and 3 can be considered.

For all other patients receiving the other moderately emetogenic chemotherapy no routine prophylaxis with dexamethasone (or equivalent corticosteroid) for days 2 and 3 is allowed for delayed nausea and vomiting.

#### 3.4.1. Study treatments

The Investigational Medicinal Product (IMP) is defined (Directive 2001/20/EC) as a pharmaceutical form of an active substance or placebo being tested or used as a reference in a clinical trial, including products already with a marketing authorisation but used or assembled (formulated or packaged) in a way different from the authorised form, or when used for an unauthorised indication, or when used to gain further information about the authorised form.

Akynzeo®, a fixed-dose oral combination (NEPA) of the NK1 Receptor Antagonist (RA) netupitant (300 mg) and of the 5-HT3 RA palonosetron (0.5 mg) is IMP in this study.

The drugs that may be used as standard of care in Arm B, including dexamethasone that is also used in Arm A, are also investigational medicinal products (IMPs) for this study.

CONFIDENTIAL

Confidential	MyRisk	Date: 05 February 2024
	Protocol	
	PROTOCOL NUMBER: IBA1160	Version: 5.1

Akynzeo® and Standard of care including dexamethasone will be used according to SmPC and will reflect the consensus of experts in the evidence-based guidelines of MASCC ESMO. The dosages are perfectly in the range of dosages specified in SmPC of these products.

Chemotherapy treatment (IV Moderately Emetogenic Chemotherapy) used in the study (alemtuzumab, azacitidine, bendamustine, carboplatin, clofarabine, cyclophosphamide, cytarabine, daunorubicin, doxorubicin, epirubicin, idarubicin, ifosfamide, irinotecan, oxaliplatin, romidepsin, temozolomide, thiopeta, trabectedin) in both arms A and B does not fall within the definition of an IMP. These products are NIMPs used to assess relevant endpoints in the clinical trial, they will not be tested.

### 3.4.2. Randomization Procedure

At randomization, patients will be stratified for:

- use and non-use of carboplatin (first stratification factor)
- country (second stratification factor)

Randomization will take place according to a computer-generated randomization list. Randomization will be performed using permuted blocks. The randomization process will be managed centrally through the eCRF.

Randomization will be performed during Visit 1 after the patient is confirmed to be eligible for the study (see section 3.6.3. Study visits procedures).

Once assigned to a treatment group before the start of cycle 1, patients will stay on the same treatment group until study completion.

### 3.4.3. Rescue medication

Rescue medication will be allowed at any time, during every cycle. Patients can ask the investigator for rescue medication. The intake of rescue medications, either prescribed or non-prescribed, must be recorded in the Patient's diary and in eCRF.

### 3.4.4. Study termination

The end of the study for each patient is defined as the day of Visit 4. Visit 4 is a visit on Day 5 of Cycle 3 or before the start of the next programmed chemotherapy cycle. Visit 4 is the final visit of the study.

### 3.4.5. Premature discontinuation

Patients may withdraw the study at any time at their own willing, without giving further details or justification.

The investigator may also exclude a subject from the study based on his/her clinical judgment:

- general or specific changes in the patient's condition which make the patient ineligible for further assessments according to the inclusion/exclusion criteria
- Non-qualification to perform consecutive cycles (e.g., for toxicity)
- Failure to return for follow-up visits

CONFIDENTIAL

Confidential	MyRisk	Date: 05 February 2024
	Protocol	
	PROTOCOL NUMBER: IBA1160	Version: 5.1

**Number of patients:** 410

**Study enrollment time:** 12 – 18 months

**Total number of visits per patient:** 5

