### 8.3. Analysis Populations Sets

The Full Analysis Set (FAS) will consist of all randomized patients to whom the investigational drug is dispensed. It will be the primary basis for the analyses of efficacy. Following the intent-to-treat principle, patients in the FAS population will be analyzed according to the treatment to which they were randomized. A Per Protocol (PP) population will consist of all patients in the FAS population who complete the study fully compliant with the protocol and without any major deviation. Patients in the PP population will be analyzed according to the treatment they received. Efficacy analyses based on the PP population will be considered supportive.

The Safety population is defined as the set of all randomized patients with at least one documented application of any study drug. It will be the basis for the analyses of safety. Patients in the Safety population will be analyzed according to the treatment they received.

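### Investigators may exclude randomised patients who no longer meet an entry criterion, and no section keeps their outcome data coming afterwards

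*Protocol*

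**What the plan says.** Protocol 3.1 describes the trial as follows: "This is a phase IV interventional, open label, randomized, active controlled, parallel arms, multicenter and multinational study". Under Protocol 3.4.5, "The investigator may also exclude a subject from the study based on his/her clinical judgment". The first ground listed is a general or specific change in condition of the kind "which make the patient ineligible for further assessments according to the inclusion/exclusion criteria". SAP 5.1 repeats the permission and its three grounds.

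The criteria that would be re-applied are in Protocol 3.3.1 and 3.3.2. They include:
- "Patients with metabolic risk factors for nausea (i.e. electrolyte imbalances causing nausea/vomiting";
- "Any illness or condition that, in the opinion of the physician, may confound the results of the study";
- "Use of olanzapine as prophylaxis of CINV";
- "Use of Standard of Care including an NK-1 RA-based regimen to prevent CINV";
- the inclusion requirement of ECOG 0 to 2.

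Only one entry criterion is expressly shielded after randomisation. Protocol 3.3.3 and 3.6.3 say that re-calculating the risk score does not affect participation. SAP 5.2 says the randomisation criteria are evaluated once, but draws from this only that the treatment arm does not change.

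On analysis, Protocol 8.3 states: "Following the intent-to-treat principle, patients in the FAS population will be analyzed according to the treatment to which they were randomized". Missing primary outcomes are multiply imputed and missing secondary outcomes use LOCF (Protocol 8.4, SAP 9.4). The Per Protocol set requires completion of the study.

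**The concern.** The clause ties the end of assessments to entry criteria, leaves the decision to someone who knows the arm, and uses criteria that can be breached because prophylaxis failed. Vomiting can be accompanied by an electrolyte disturbance. ECOG can fall after a bad cycle. The open clause on confounding conditions can be applied to almost any deterioration.

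The primary endpoint is complete response in each of three cycles, read from MAT, diary and rescue records. Under Protocol 3.6.3 these papers come back at the next cycle's visit, or at Visit 4 for cycle 3. No early-termination visit or diary retrieval is described. A patient excluded between visits may therefore leave with the record of the failing cycle. If exclusion is related to failure and differs by arm, the missing data no longer fit the MCAR/MAR assumption in Protocol 8.2 and 8.4, and the treatment comparison can move in either direction.

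**Working it through.** **1. The plan's own figure.** Inputs from Protocol 8.2: 71% versus 60%, two-sided alpha 0.05, power 80%, correlation 0.5, and missing proportions 0, 7.5 and 15%, so the observed proportions are p = 1, 0.925, 0.85.
- Variance factor = [Σp + ρ·Σ(j≠k) p_j p_k] / (Σp)² = (2.775 + 0.5 × 5.1225) / 2.775² = 0.693.
- log OR = ln[(0.71/0.29)/(0.60/0.40)] = ln 1.632 = 0.490.
- N = 2(1.960 + 0.842)² × 0.693 × [1/(0.71×0.29) + 1/(0.60×0.40)] / 0.490² = 409, against the stated 410.
- Completers: 410 × 0.85 = 348.5, against the stated 348.

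The sample size is sound on its inputs. One of those inputs is MCAR/MAR missingness.

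**2. What the imputation can see.** The PROC MI code in SAP 9.4.1 uses treatment, carboplatin, country and the three cycle outcomes. It does not use the reason for removal. There are two cases:
- The failed cycle is recorded and later cycles are missing. Removal then depends on a recorded outcome and arm, which is MAR given the model.
- The failed cycle is lost too. The value that drove the removal is unobserved, which is MNAR.

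**3. Size in each case.** I simulated monotone logistic imputation with 5 imputations, followed by a Wald test on the log odds ratio with between-patient variance. Settings: N = 410, exchangeable correlation 0.5, 1,500 trials per scenario for rejection rates, and 200,000 patients per arm for the rates. Carboplatin and country were left out. A patient who fails a cycle is removed with the probability shown; these probabilities are assumptions, as the documents give none.

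| True CR, NEPA/control | Removal after a failed cycle | Failed cycle's data | Imputed CR | Difference (points) | Rejection |
|---|---|---|---|---|---|
| 71/60 | none; 7.5% random attrition per cycle | – | 71.1/60.1 | +11.0 | 81.5% |
| 60/60 | 10%, NEPA only | kept | 60.0/60.0 | 0.0 | 4.5% |
| 60/60 | 20%, NEPA only | kept | 60.0/60.1 | −0.1 | 4.8% |
| 60/60 | 10%, NEPA only | lost | 63.2/59.9 | +3.3 | 11.7% |
| 60/60 | 20%, NEPA only | lost | 66.6/59.9 | +6.7 | 34.0% |
| 71/60 | 10%, control only | lost | 71.0/63.1 | +8.0 | 51.7% |
| 71/60 | 20%, control only | lost | 71.1/66.2 | +4.9 | 21.4% |
| 71/60 | 20%, NEPA only | lost | 76.3/60.0 | +16.3 | 98.5% |

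At 10% with the cycle lost, the shift is +3.3 points under no effect (NEPA-only removal) and 8.0 − 11.0 = −3.0 points under the planned effect (control-only removal). Equal 20% removal in both arms leaves the null difference near zero (66.2 versus 66.4) but raises both rates by about 6 points.

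**4. Scale against the plan.** In the 10% NEPA-only, cycle-lost scenario, the affected arm has 4.0, 7.7 and 11.2% missing, an average of 7.6%. The plan allows (0 + 7.5 + 15)/3 = 7.5% from all causes. In the corresponding 20% scenario the figures are 8.0, 14.8 and 20.7%, an average of 14.5%. The 20% rows where the cycle is lost should be read as extreme.

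**5. Other analyses.** LOCF can carry a cycle 1 success over an unreturned cycle 2 failure. Excluded patients leave the Per Protocol set by definition, and with it the risk-factor analysis in SAP 9.8. The pre-global country summary in SAP 9.9 reports the primary endpoint only for patients with complete data in all three cycles.

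**The case against.** A reader might infer that failing patients vanish from the primary analysis. On that reading, simple deletion of 10% of failing cycles would lift the control rate from 60% to 0.60/(0.60 + 0.40 × 0.90) = 62.5%. The documents do not support this. The FAS keeps every randomised patient to whom drug was dispensed, and missing cycles are imputed using the other cycles' outcomes.

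A reader might also infer a one-sided trigger: adding an NK-1 RA after a failed cycle would breach a criterion only in Arm B, and olanzapine in either arm. But the clause speaks of changes in the patient's condition, and a change of prophylaxis fits that on only one reading. Even the electrolyte criterion is worded with the imbalance as cause of the vomiting, not its result, although an investigator facing both may not separate them.

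There are partial safeguards:
- At Visits 2 and 3 the diary and MAT are collected, checked and completed with the patient. A removal decided there leaves the failed cycle on record, the case in which imputation showed no bias.
- Rescue use must also be entered in the eCRF (Protocol 3.4.3), lack of efficacy is recorded (10.3.1), and patients are called between days 3 and 5.
- SAP 8.2 already treats a violated criterion as a monitored deviation.
- Protocol 3.7 and the HEOR part of the Study Summary follow resource use for the study duration and name only death, withdrawal of consent and loss to follow-up as ending it.

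These points stand and limit the harm. They do not close the gap: none requires emesis data after an investigator exclusion, and the HEOR rule does not fit 3.4.5, because investigator exclusion is not on its list.

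**Conclusion.** The clause should be fixed, but it is not evidence that the primary result is biased. The primary analysis is exposed only if the failing cycle's data are not retrieved, or if removal depends on something the imputation model lacks, such as unrecorded severity. The 3-point shift rests on an assumed 10% removal rate, confined to one arm, with the failed cycle lost; it scales with that rate and disappears when the cycle is kept. The permission is discretionary, and the documents do not show its frequency or direction, so no sign can be given to the bias. The clearest criteria are electrolyte imbalance, the open clause on confounding conditions and ECOG. No sensitivity analysis for data missing not at random is specified, although MVTF (missing value treated as failure) is in both abbreviation lists.

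**What to change.** In Protocol 3.4.5 and SAP 5.1, separate stopping study treatment from stopping outcome collection:
- No longer meeting an entry criterion after randomisation is recorded as an event or deviation, in line with SAP 8.2, and does not by itself end outcome assessment.
- Diary, MAT and rescue data are retrieved for the current cycle and collected for every later study cycle of chemotherapy received. The exceptions are withdrawal of consent, death, loss to follow-up, or discontinuation required by another section, such as pregnancy in Protocol 10.3.2.
- Reasons for investigator exclusion are tabulated by arm.
- A sensitivity analysis of the primary endpoint counts missing cycles after investigator exclusion as failures, or uses delta-adjusted multiple imputation.

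Reconcile 3.4.5 with the follow-up rule in Protocol 3.7 and the Study Summary. Simply deleting the ground for exclusion, or closing the list of reasons for ending collection, would conflict with the pregnancy rule and touch clinical stopping. Treatment and safety decisions stay with the investigator.

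The cost is wording, one table, one sensitivity analysis and a few more diaries from patients already attending for chemotherapy. The downside is that some cycles will be observed under changed prophylaxis; they are analysed as randomised, and the Per Protocol analysis is already planned as support. If enrolment has ended, the table and the sensitivity analysis can still be added before database lock.
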